8.5.3. Tumor Biopsy

For subjects in Phase 1 monotherapy, tumor biopsy at screening and Cycle 2 Day 1 are optional. For subjects treated in Phase 1 combination and Phase 2, a tumor biopsy at screening and in Cycle 2 as indicated in Table 5 are required. If the investigator considers that performing a tumor biopsy at Cycle 2 puts a subject at undue safety risk and the subject is otherwise eligible to continue study participation, the subject may be allowed to continue the study. Additionally for Phase 2, the Sponsor may elect to permit subjects on study who do not have lesions amenable to biopsy in the investigator's judgement but would otherwise be eligible for the study following discussion with the investigator. The reason for not performing a required biopsy will be documented in the CRF.

An archival tumor tissue sample is required for all subjects. A fresh tumor biopsy is permissible at screening if tumor tissue from a subject's previous biopsy cannot be obtained.

Table 6 Collection time point requirements for tumor biopsy

	Phase 1 monotherapy	Phase 1 combination	Phase 2
Archival Biopsy Sample	X	X	X
Screening	Optional	X	X
Cycle 2	Optional: Cycle 2 Day 1 post-dose + 4 days	Cycle 2 Day 1 post-dose + 4 days	Cycle 2 Day 1 or Day 8 post dose ^a

^aThe biopsy should be performed on Day 2 or 3 if performed post Cycle 2 Day 1 E-602 administration or Day 9 or 10 if performed post Cycle 2 Day 8 E-602 administration.

During screening and during Cycle 2 as indicated in Table 6, subjects who undergo a tumor biopsy will have a sample collected and preserved in a representative formalin-fixed paraffin-embedded (FFPE) block (preferred) or at least 20 unstained, freshly cut, serial sections (on slides) from an FFPE tumor specimen will be collected. The specimen should be accompanied by the associated pathology report. The following specimen types are acceptable: resections, core needle biopsies, excisional, incisional, or forceps biopsies. For core needle biopsy specimens, preferably, at least 3 cores embedded in a single paraffin block should be submitted for evaluation. Fine needle aspirate is not an acceptable tissue collection method.

Tumor cells will be analyzed for immune modulation of different immune cell subtypes, including T cells, macrophages, dendritic cells, and neutrophils. The following analyses may include but is not limited to:

- Tumor desialylation by immunohistochemistry (IHC)
- Tumor IHC analysis for immune markers (PD-L1) and modulation of different immune cell subtypes (T cells, macrophages, DC, neutrophils)

These samples may also be used for other biomarker research to further elucidate E-602 mechanism of action, identify potential resistance mechanisms, understand variability in response and/or adverse events, identify other biomarkers of response, and to better understand the disease

under study. Additional exploratory biomarkers related to tumor and immune biology may be analyzed, using methods such as gene expression profiling, mutational, protein and tissue image analysis.

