- 16. Radiology examination of tumors includes contrast-enhanced CT (preferred) or MRI imaging of the chest, abdomen, and pelvis. The same method (CT, PET/CT, MRI) and the same technique should be used to characterize each identified and reported lesion at screening and during the study. Radiology examinations will be performed during screening (permitted up to 35 days prior to Cycle 1, Day 1), 9 weeks (±1 week) after the first dose and every 9 weeks (±1 week) thereafter, regardless of any study treatment(s) delay. An EOT examination should be performed unless the subject already has radiographic confirmation of PD ≤4 weeks prior to the EOT visit. For ovarian cancer subjects, at each radiology examination, CA-125 should also be tested.
- 17. See Section 8.5 for further information on sample collection and analyses.
- 18. Biomarkers of disease may be performed up to 72 hours prior to Day 1 as follows: carcinoembryonic antigen (CEA) and CA-125 for subjects with NSCLC, CEA and CA19-9 for subject with colorectal or pancreatic cancer, and CA-125 for subjects with ovarian cancer.
- 19. Circulating tumor DNA samples will be collected with radiological assessments. See Footnote 16.
- 20. Tumor biopsy is optional at screening and on Cycle 2 Day 1 (+4 days) during Phase 1. An archive tissue sample is required for all subjects. See Section 8.5.3 for further information.
- 21. Dosing visits should not be skipped due to dose delays.

1.3.2. Phase 1 Combination Dose Escalation and Backfill; Phase 2 E-602 Monotherapy and Combination

1.3.2. Phase 1 Combination Do	ose Escala	tion a	nd E	Back	fill; I	Phase	e 2 E	-602	Mo	notl	1er	apy	and	l Co	mb	inatio	n		
Study Period						7	Γreat	ment	[21]								ost Tr	eatme	at
Cycle or Visit	Screen			Cycle	1 [1]				Cycl	Cycle 2 [1]			Cycle ≥3			EOT [2]			
Day	-28 to -1	1	2	3	8	9	15	1	8	9	10	15	1	8	15		+30D	+90D	Q3M [4]
Visit Window (days)		-	-	-	±2	-	±2	±2	±2	-	-	±2	±2	±2	±2	+14	±7	±7	±7
Clinical Assessments																			
Written informed consent [5]	X																		
Performance status [6]	X	X			X			X					X			X	X	X	
Concomitant medications [7]	X	X			X		X	X	X			X	X	X	X	X	X	X	
Height (cm)	X																		
Weight (kg) [8]	X	X			X		X	X	X			X	X	X	X	X			
Vital signs/oxygen saturation [9]	X	X			X		X	X	X			X	X	X	X	X	X		
Medical history [10]	X																		
Adverse event assessment		X			X		X	X	X			X	X	X	X	X	X	X	
12-lead ECG	X																		
Study Treatment																			
E-602 administration		X			X		X	X	X			X	X	X	X				

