- 20. Fresh tumor biopsy is required for all subjects in Phase 1 combination at screening and on Cycle 2 Day 1 post-dose (+4 days). Fresh tumor biopsy is required for all subjects in Phase 2 at screening and post-dose on Cycle 2 Day 1 or Day 8. The biopsy should be performed on Day 2 or 3 if performed post Cycle 2 Day 1 E-602 administration or Day 9 or 10 if performed post Cycle 2 Day 8 E-602 administration. An archive tissue sample is required for all subjects. See Section 8.5.3 for further information.
- 21. Dosing visits should not be skipped due to dose delays.
- 22. Unscheduled cytokine panel samples should be collected in the event of an infusion related reaction.

2. Introduction

E-602, also known as Bi-Sialidase,

E-602 is being developed as an immune therapy to treat

advanced cancers.

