Each treatment cycle consists of 21 days. E-602 will be administered on Days 1, 8, and 15 of each cycle. Cemiplimab, if given, will be administered on Day 1 of each cycle. When the cemiplimab combination is administered, cemiplimab should be administered first and E-602 administered at least 30 minutes after the cemiplimab infusion is completed. Subjects receiving ≥10 mg/kg of E-602 as monotherapy or in combination with cemiplimab should receive premedication including antihistamines and acetaminophen as indicated in the Pharmacy Manual. Corticosteroids should be used as premedication for subjects with previous infusion reaction(s) to E-602 as indicated in the Pharmacy Manual (see Pharmacy Manual, Section 10.5).

Dose escalation guidelines for all Phase 1 dose cohorts will utilize a modified 3+3 design. Assessments of DLTs will occur during Cycle 1 (defined as a subject receiving 3 doses of E-602 for monotherapy cohorts and 3 doses of E-602 and 1 dose of cemiplimab for combination therapy cohorts) for all dose cohorts. Safety monitoring for immune-related toxicities will continue for all

subjects for 90 days after treatment discontinuation unless a subsequent cancer therapy is started. All available data will be taken into consideration in selecting the RP2D.

E-602 dose escalation will continue until the MTD is exceeded, unacceptable toxicity is reached, or the RP2D is determined. The Sponsor may terminate dose escalation at an RP2D prior to reaching the MTD based on emerging PK, pharmacodynamic, and safety data.

Any Phase 1 cohort may be backfilled at the judgement of the Sponsor, up to a total of 15 subjects in the dose cohort (dose escalation and backfill) as needed to obtain additional safety, PK, and pharmacodynamic data at a particular dose level.

In addition to DLTs, subjects will be evaluated for safety and tumor response as well as PK and pharmacodynamics, as listed in the Schedule of Activities (SoA) in Section 1.3.

Phase 2: Dose Expansion, Monotherapy and Combination Therapy

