- Changes in the glycoproteomic profile

These samples may also be used for other biomarker research to further elucidate E-602 mechanism of action, identify potential resistance mechanisms, understand variability in response and/or adverse events, identify other biomarkers of response, and to better understand the disease understudy. Analyses may include, but are not limited to protein, metabolite and antibody profiling methodologies.

Additional exploratory biomarkers related to tumor and immune biology may be analyzed, using methods such as gene expression profiling, mutational, protein and tissue image analysis.

^bThe 0.5 h sample collection is \pm 5 mins from the end of E-602 infusion. In instances when the infusion time is >30 minutes, the \pm 5 mins window still applies to the end of the infusion.

^{&#}x27;In the event the E-602 infusion exceeds 2 hours, the 2 h timepoint will be permitted as a missed assessment.

^dThe 6 h sample is only required for Phase 1 E-602 monotherapy cohorts.

^eCycle 1 Day 3 and Cycle 2 Day 10 sample collection is not required for Phase 2.

Details of sample collection, storage, and shipping instructions will be provided in the Laboratory Manual.

Table 4 Phase 1 E-602 monotherapy biomarker sample collection time points for pharmacodynamic, genetic and immunogenicity analyses

Cycle	Day	Time ^a	Cytokine Panels and C3a	FACS (desialylation and activation)	RNASeq (blood)	Circulating Tumor DNA	Tumor Biopsy	ADA	Glycoproteomic Profile
Screening							X		
1	1	predose	X ^b	Xb	X ^b	Xb		X	X
	2	$24\ h\pm 2\ h$	X	X	X				X
	3	$48\ h\pm 4\ h$	X	X	X				X
	8	predose	X	X	X				X
	9	$24\ h\pm 2\ h$	X	X	X				X
	10	$48\ h\pm 4\ h$	X	X	X				X
	15	predose	X	X	X				X
2	1 (Day 22)	predose					X	X	
≥ 3	1	predose				Xc		X	
EOT	NA	NA						X	
Follow- up 30 day	NA	NA						X	

^aAll time points except predose are after the start of infusion.

Table 5 Phase 1 combination and Phase 2 biomarker sample collection time points for pharmacodynamic, genetic and immunogenicity analyses

Cycle	Day	Time ^a	Cytokine Panels and C3a	(desialylation	SNPs	Circulating Tumor DNA	Tumor Biopsy	ADA	Glycoproteomic Profile
Screening							X^d		
1	1	predose	X ^b	X^b	X	Xb		X	X
	2	24 h ± 2 h	X	X					X
	8	predose	X	X					X
	9	24 h ± 2 h	X	X					X
	15	predose	X	X			_		X

^bTwo predose samples should be collected at least 1 hour apart and up to 72 hours prior to Cycle 1 Day 1.

^cCirculating tumor DNA samples will be collected with radiological assessments.

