6.8.1.2 Pharmacodynamic Biomarker Analysis

Immunophenotyping (FACS), Chemokine Panel, Pro-inflammatory Panel and C3a biomarkers will be summarized using descriptive statistics for select parameters including absolute measurements and fold change from baseline by visit. Tissue IHC biomarkers will be summarized using descriptive statistics for select parameters including absolute measurements and change from baseline.

Sensitivity pharmacodynamic biomarker analyses may also be performed. For Tissue IHC biomarkers, data may be summarized for the patients for which there are matched pre- and on-treatment and the on-treatment biopsy was collected within 48 hours after the last dose of E-602. All biomarker results will be presented in a by-subject listing.

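### For Phase 1 monotherapy, Table 4 puts the optional Cycle 2 Day 1 tumor biopsy before the dose and Table 6 puts it after; the main tumor IHC summary has no timing limit to separate the two.

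*Protocol*

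**What the plan says.** Four places in the protocol bear on when the Phase 1 monotherapy Cycle 2 biopsy is taken.

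- **Table 4** (Section 8.5.1), titled "Phase 1 E-602 monotherapy biomarker sample collection time points for pharmacodynamic, genetic and immunogenicity analyses", has its own Tumor Biopsy column. Its Cycle 2 row reads "1 (Day 22) predose X X", the marks being for biopsy and ADA. Its footnote a sets predose rows apart from those timed after the start of infusion. No footnote qualifies the biopsy mark.
- **Table 6** (Section 8.5.3) gives "Optional: Cycle 2 Day 1 post-dose + 4 days" for the same subjects.
- **Footnote 20 of the monotherapy Schedule of Activities** (Section 1.3.1) says "Tumor biopsy is optional at screening and on Cycle 2 Day 1 (+4 days) during Phase 1". It does not say before or after the dose, and it refers the reader to Section 8.5.3.
- **Section 8.5.3** points to Table 6 for the Cycle 2 sample: "During screening and during Cycle 2 as indicated in Table 6, subjects who undergo a tumor biopsy will have a sample collected".

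Table 5, for the Phase 1 combination and Phase 2 cohorts, uses the same predose row, but each biopsy mark carries footnote d, which moves the Cycle 2 biopsy to after the dose.

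In the SAP, Section 6.8.1.2 summarizes tissue IHC descriptively, as absolute values and change from baseline, with no limit on time since dose. The same section allows an optional sensitivity summary restricted to matched pairs where "the on-treatment biopsy was collected within 48 hours after the last dose of E-602".

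**The concern.** A site working from Table 4 and a site working from Table 6 would both be following the protocol, yet would take tissue at different points in the dosing interval. One sample is taken at the end of a weekly interval, the other in the first days after a dose. If the tumor effect of E-602 changes over the week, these samples do not measure the same quantity.

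What is at stake is the tumor pharmacodynamic comparison across monotherapy dose levels. Change in tumor desialylation by IHC is the listed exploratory endpoint for the drug's enzymatic effect in tumor tissue, and protocol Section 4.2 bases the monotherapy RP2D on safety, pharmacodynamic and PK data taken together. Cohorts are 3 to 6 subjects, at most 15 with backfill, and the biopsy is optional. One or two samples taken at a different time could therefore shift a dose-level summary.

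**Working it through.** **Inputs.** The cycle is 21 days, and the dosing rule is "E-602 will be administered on Days 1, 8, and 15 of each cycle" (Section 4.1.1). The visit windows are ±2 days for Cycle 1 Day 15 and ±2 days for Cycle 2 Day 1 (Section 1.3.1). Table 6 allows up to 4 days after the dose. The SAP sensitivity limit is 48 hours.

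**Step 1: reproduce the plan's figure.** Cycle 2 Day 1 = 21 + 1 = Day 22, which agrees with Table 4.

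**Step 2: time since last dose if Table 4 is followed.** The last Cycle 1 dose is on Day 15.
- Nominal: 22 − 15 = 7 days.
- Shortest with windows: (22 − 2) − (15 + 2) = 3 days = 72 h.
- Longest with windows: (22 + 2) − (15 − 2) = 11 days = 264 h.

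**Step 3: time since last dose if Table 6 is followed.** 0 to 4 days = 0 to 96 h after the Cycle 2 Day 1 dose.

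**Step 4: would the SAP separate the two?**
- The pharmacodynamic population (SAP Section 3.5) needs one baseline and one post-baseline value, so a predose Cycle 2 Day 1 biopsy qualifies.
- The only IHC exclusion (SAP Section 6.8.1.1) is inadequate tissue on H&E. Timing is not a criterion.
- The main IHC summary (SAP Section 6.8.1.2) therefore takes both kinds of sample.
- The optional 48-hour summary would drop every predose biopsy when dosing is on schedule, because the shortest gap is 72 h and 72 > 48. It would also drop biopsies that comply with Table 6 but are taken between 48 and 96 h, so it cannot stand in for a defined main analysis.

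**Step 5: does any footnote settle it?** Table 5 shows the same layout with a correcting footnote; Table 4 has none. Footnote 20 leaves the question open and sends the reader to Section 8.5.3, which leads to Table 6. But footnote 17, attached to the whole biomarker block of the Schedule of Activities, sends the reader to all of Section 8.5, which contains both tables.

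**The case against.** The strongest reply is that the documents largely show which table was meant to govern. Section 8.5.1 introduces Tables 4 and 5 for blood and serum samples; biopsy has its own section and its own table; and a forward window of four days fits poorly with a predose sample. Table 4 then looks like Table 5's layout with the footnote left off. Much of this stands, and it makes divergence between sites less likely. It does not remove the conflict. Table 4 carries a biopsy column, and Section 8.5.3 itself relies on Table 5, Table 4's counterpart, for the Cycle 2 biopsy in the other cohorts.

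The second reply is that little depends on the result. The biopsy is optional and the endpoint is exploratory and descriptive. No passage gives tumor IHC a specific role in choosing the RP2D. Section 4.3.1 names immune-cell desialylation as the critical pharmacodynamic indicator, and that is measured in blood by FACS, which biopsy timing does not affect. This stands and limits the severity.

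Two stronger readings are tempting. A reader might infer that the tumor result does mix the two kinds of tissue. The documents show only that it could; nothing in them shows that any site took a predose biopsy. A reader might also try to size the bias from the monkey accumulation ratios in Section 2.2.1.2. Those ratios (0.805 to 1.04) cover weekly and twice-weekly dosing together and describe plasma exposure. The documents give neither human decay nor the rate at which tumor sialylation recovers, so no percentage can be derived.

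**Conclusion.** The conflict between Table 4 and Table 6 is real, lies in current text, is specific to Phase 1 monotherapy, and is not resolved by any footnote to Table 4. It is more than a typographical slip, because the two instructions lead to tissue nominally 7 days after a dose or 0 to 4 days after one, and the main IHC summary would pool them.

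The consequence is conditional. It requires that sites acted on different tables and that the tumor effect changes within the weekly interval; the documents establish neither. The 3-to-11-day range assumes dosing within the visit windows, and delays would lengthen it. The effect on the mean change from baseline cannot be derived from the documents. Sample size, error rates and safety rules are unaffected. Severity: minor. Which time point is right is for the sponsor to state.

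**What to change.** In the protocol, reconcile Table 4, footnote 20 in Section 1.3.1 and Table 6 so that one biopsy time applies to Phase 1 monotherapy, and add a footnote to the biopsy mark in Table 4 stating it, as Table 5 does.

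In SAP Section 6.8.1.2, list hours since the last E-602 dose for each on-treatment biopsy. Summarize biopsies taken outside the reconciled window separately from the main on-treatment IHC summary. This also covers tissue already collected, whichever time is confirmed.

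The cost is one footnote, matching wording in the Schedule of Activities and a few lines in the SAP. No extra biopsies are needed. The drawback is slightly fewer samples in the main summary, with the rest still shown in their own row.

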8.6. Immunogenicity Assessments

Antibodies to E-602 will be evaluated in plasma samples collected from all subjects according to the SoA. These samples will be collected pre-dose at the designated visits, including a pre-dose sample before the initial dose on Cycle 1 Day 1.

The detection and characterization of the ADAs will be performed using a validated assay method.

9. Statistical Considerations

The statistical analysis plan (SAP) will be finalized prior to database lock and will include a more technical and detailed description of the statistical analyses described in this section. This section is a summary of the planned statistical analyses of the most important endpoints including primary and key secondary endpoints.

9.1. Analysis Sets

DLT Evaluable Set:

Will include all subjects treated in the dose escalation part who have had a DLT within Cycle 1 on study or without a DLT but completed safety assessments through Cycle 1 (3 doses of E-602 administered for monotherapy cohorts and 3 doses of E-602 and 1 dose of cemiplimab administered for combination therapy cohorts). The DLT Evaluable Set will be defined for each dose cohort. Subjects who discontinue prior to completing Cycle 1 (3 doses of E-602 administered for monotherapy cohorts and 3 doses of E-602 and 1 dose of cemiplimab administered for combination therapy cohorts) for reasons other than toxicity may be replaced.

Safety Analysis Set:

Will include all subjects who have received any dose of study treatment. The Safety Analysis Set will be used for safety analyses. Safety Analysis Set may be further defined by the phase of the study, dose, and tumor type.

Efficacy Evaluable Set:

Will include all subjects who receive any dose of study treatment, meet eligibility criteria, have measurable tumor lesions at baseline, and have at least one post-baseline disease assessment per RECIST v1.1. Efficacy Evaluable Set is defined for each cohort in the Phase 2 separately.

Pharmacokinetics (PK) Analysis Set:

Will include all subjects in the Safety Analysis Set for whom adequate data on E-602 plasma concentration are available.

9.2. Statistical Analyses

9.2.1. General Considerations

The statistical analyses will generally be descriptive in nature. Data collected will be presented using summary tables, data listings, and figures. For continuous variables, descriptive summaries will include the mean, median, standard deviation, the first and third quartiles, minimum, and maximum. For categorical variables, the number and percentage of subjects in each category will be presented.

9.2.2. Subject Disposition

The number and percent of subjects who have consented, treated, discontinued (including reasons for discontinuation), and completed the study will be summarized. The number of subjects for each analysis set will be tabulated.

9.2.3. Baseline Characteristics

Descriptive summary statistics will be provided for demographic variables (age at consent, sex at birth, race, ethnicity) and baseline disease characteristics (e.g., ECOG performance status). Relevant medical history and prior anti-cancer therapies/medications will also be summarized.

9.2.4. Safety Analyses

9.2.4.1. Treatment Exposure

Duration of treatment, cumulative dose administered, relative dose intensity, frequency of dose adjustment, and treatment discontinuation will be summarized. For the combination therapy cohorts, E-602 and cemiplimab doses will be summarized separately.

9.2.4.2. Treatment Emergent Adverse Events

All adverse events will be coded to a system organ class and a preferred term based on the Medical Dictionary for Regulatory Activities (MedDRA) version 24.0 or later.

Treatment-emergent adverse events (TEAEs) are defined as AEs with an onset date on or after the date of first dose of study treatment until 90 days after the last dose.

Subject incidence of all treatment-emergent adverse events, serious adverse events, adverse events leading to discontinuation of treatment, and fatal adverse events will be tabulated by system organ class and preferred term.

The number and percent of subjects reporting TEAEs will be evaluated overall and by dose level and will also be tabulated by severity and relationship to study treatment. The severity of each adverse event will be graded using The Common Terminology Criteria for Adverse Events (CTCAE) version 5.0 or later criteria.

For the Phase 1 component of the study, DLTs (if any) will be summarized by dose and will be listed separately.

